- OCTs obtained for enrollment into the run-in phase of the study eye may be sent to a centralized reading center for grading, although participant eligibility is determined by the site (i.e., individuals deemed eligible by the investigator will be enrolled into run-in phase without pre-enrollment reading center confirmation). Subsequently, if the reading center determines that the automated CSF reading by the OCT machine is inaccurate, and manual adjustment of the CSF thickness on OCT is less than the OCT eligibility criteria, the eye will be dropped from the run-in phase.
- 647
- Electronic-ETDRS visual acuity testing at 3 meters using the Electronic Visual Acuity
 Tester (including protocol refraction) in each eye. (within 8 days prior to enrollment)
- 650
- This testing procedure has been validated against 4-meter ETDRS chart testing.⁴⁵
- 651 2. OCT on study eye (within 8 days prior to enrollment and at least 21 days after any prior
 652 intravitreal anti-VEGF treatment)
- 653 3. Ocular examination on each eye including slit lamp, measurement of intraocular pressure,
 654 lens assessment, and dilated ophthalmoscopy (within 8 days prior to enrollment)
- 655 4. Measurement of blood pressure
- 656

657 2.4 Enrollment of Eligible Study Participants into Run-In Phase

Prior to enrollment, the study participant's understanding of the trial, willingness to accept
 the assigned treatment group at the end of the run-in phase, and commitment to the follow-up
 schedule should be reconfirmed.

- 661 2. The initial run-in injection(s) must be given on the day of enrollment; therefore, a study
- 662 participant should not be enrolled until this is possible. For study participants with two study 663 eyes, both eyes must be treated on the day of enrollment. If the investigator is not willing to
- 664 perform bilateral injections on the same day, only one eye should be enrolled.

665 666	Chapter 3. RUN-IN PHASE
667	
668	3.1 Overview
669	Each study eye is required to complete a 12-week run-in phase. The run-in phase will identify
670	study eyes that truly have persistent DME despite anti-VEGF therapy by requiring an additional 3
671	injections while also collecting standardized visual acuity and OCT measurements. This chapter
672	describes visit schedules, procedures and treatment during the run-in phase of the study.
673 674	3.2 Visit Schedule
675	The schedule of protocol-specified follow-up visits during the run-in phase is as follows:

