676	The schedule of protocol-specified follow-up visits during the full-in phase is as follows.
677	• 4 weeks (± 1 week)
678	 8 weeks (±1 week)
679	 12 weeks (±1 week) – randomization visit
680	• 12 weeks (±1 week) Tunuomization visit
681	A minimum of 21 days is required between visits.
682	
683	3.3 Testing Procedures During the Run-In Phase
684	The following will be performed at the 4-week and 8-week run-in phase visits:
685	
686 687	1. Electronic-ETDRS visual acuity testing at 3 meters using the Electronic Visual Acuity Tester in each eye, including protocol refraction in the study eye
688	2. OCT on study eye
689 690	3. Ocular examination on study eye including slit lamp, measurement of intraocular pressure, lens assessment, and dilated ophthalmoscopy
691 692	All of the testing procedures do not need to be performed on the same day, provided that they are completed within the time window of a visit and prior to initiating any retreatment.
693	
694	Testing procedures at the 12-week visit to assess eligibility for the randomization phase are
695	detailed in section 4.3.
696	
697	3.4 Treatment During the Run-in Phase
698	All study eyes will receive an injection of ranibizumab 0.3 mg at enrollment, 4 weeks, and 8
699	weeks. The injections must be at least 21 days apart. If an eye experienced adverse effects from
700	a prior intravitreal injection during the run-in phase precluding future injections or additional
701	injections are otherwise contraindicated according to the investigator (e.g. DME is no longer
702	present), the eye will not continue in the study.
703	
704	3.4.1 Anti-VEGF Drug
705	Ranibizumab 0.3 mg (Lucentis [®]) will be the anti-VEGF drug that will be used in the study, both

during the run-in phase and post-randomization. The physical, chemical and pharmaceutical
 properties and formulation will be provided in the Ranibizumab Clinical Investigator Brochure.

708

709 **3.4.2 Intravitreal Injection Technique**

- 710 The injection is preceded by a povidone iodine prep of the conjunctiva. Antibiotics in the pre-,
- 711 peri-, or post-injection period are not necessary but can be used at investigator discretion if such
- 712 use is part of his/her usual routine.
- 713
- 714 The injection will be performed using sterile technique. The full injection procedure is described
- 715 in the DRCR.net Study Procedures Manual.
- 716

717 **3.4.3 Deferral of Injections Due to Pregnancy**

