- Female study participants must be questioned regarding the possibility of pregnancy prior to
- reach injection. In the event of pregnancy, study injections must be discontinued.

720	Chapter 4.
721	RANDOMIZATION PHASE
722	
723	4.1 Overview
724	After completing the run-in phase of the study, eligibility criteria for the randomization phase
725	will be assessed for enrolled eyes at the 12-week run-in visit ("randomization visit"). This
726	chapter describes randomization, testing procedures, and follow-up visit and treatment schedules
727	during the randomization phase.
728	
729	4.2 Eligibility Criteria for Randomization
730	Once the run-in phase has been completed, the study participant must have at least one eye
731	meeting all of the inclusion criteria and none of the exclusion criteria listed below, confirmed at
732	the 12-week run-in visit ("randomization visit") to be eligible for randomization. A study
733	participant may have two study eyes only if both are eligible at the time of randomization.
734	
735	Inclusions
736	a. All 3 run-in phase visits and ranibizumab injections were completed within ± 10 days of the
737	target visit date.
738	b. Randomization visit no more than 5 weeks (35 days) from 8-week visit.
739	c. At least 21 days since prior study injection.
740	d. Visual acuity letter score in study eye ≤ 78 and ≥ 24 (approximate Snellen equivalent 20/32 to 20/220)
741 742	20/320)
742	e. On clinical exam, definite retinal thickening due to DME involving the center of the macula.f. CSF thickness (microns) on OCT meeting either one of the following two gender- and OCT
744	machine-specific criteria:
745	i. Zeiss Cirrus: ≥290 in women; ≥305 in men
746	ii. Heidelberg Spectralis: \geq 305 in women; \geq 320 in men
747	in Therabileting Speenland, _500 in Women, _520 in men
748	Exclusions
749	g. All participant-level exclusion criteria in section 2.2.1 must not have developed or occurred
750	during the run-in phase.
751	h. All study eye-level exclusion criteria in section 2.2.2 (except the criterion for prior anti-
752	VEGF treatment) must not have developed or occurred during the run-in phase.
753	
754	4.3 Randomization Visit Testing Procedures
755	The following procedures are needed to assess eligibility for randomization and/or to serve as
756	baseline measures for the study analyses.
757	
758	• The testing procedures are detailed in the DRCR.net Procedures Manuals (Visual

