759	Acuity-Refraction Testing Procedures Manual, and Study Procedures Manual).
760	Visual acuity testing, ocular exam, and OCT will be performed by DRCR.net
761	certified personnel.
762	• OCTs meeting DRCR.net criteria for manual grading may be sent to a reading center
763	but study participants' eligibility is determined by the site (i.e., individuals deemed
764	eligible by the investigator will be randomized without pre-randomization reading
765	center confirmation).
766	

767 768	1.	Electronic-ETDRS visual acuity testing at 3 meters using the Electronic Visual Acuity Tester (including protocol refraction) in each eye. (on day of randomization)
769		• This testing procedure has been validated against 4-meter ETDRS chart testing. ⁴⁵
770	2.	OCT on study eye (on day of randomization)
771 772	3.	Ocular examination on each eye including slit lamp, measurement of intraocular pressure, lens assessment, and dilated ophthalmoscopy (on day of randomization)
773	4.	Laboratory Testing- HbA1c
774 775 776		• HbA1c does not need to be repeated if available in the prior 3 months. If not available at the time of randomization, the individual may be enrolled but the test must be obtained within 3 weeks after randomization.
777 778 779	5.	Measurement of blood pressure
780	4.4	4 Randomization of Eligible Study Participants
781 782 783	1.	
784 785 786 787 788	2.	The baseline injections must be given on the day of randomization; therefore, a study participant should not be randomized until this is possible. For study participants with two study eyes, both eyes must be treated on the day of randomization. If the investigator is not willing to perform bilateral injections on the same day, only one eye should be randomized.
789 790 791		• Study participants with one study eye will be randomly assigned, with equal probability, to receive either:
792 793 794		 Group A: Sham + intravitreal ranibizumab 0.3 mg Group B: Intravitreal dexamethasone +intravitreal ranibizumab 0.3 mg
795		Randomization will be stratified by two factors:
796		1. Presence or absence of improvement in retinal thickness during the run-in phase,
797		defined as reduction in CSF thickness by 10% at any run-in visit, compared with the
798 799		prior visit.2. Presence or absence of improvement in visual acuity during the run-in phase, defined
800		as 5 or more letter gain in visual acuity at any run-in visit, compared with the prior
801		visit.
802		

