 - Footnote No. of missing values and No. of values truncated at 3 standard deviation from the mean (if any)¹
 - Review lens status for eyes improved or worsened on visual acuity at 24 weeks [Discussion text]
 - iii. Area under the curve (AUC) between randomization and 24 weeks using truncated data [Figure 2]
 - Mean \pm SD
 - Median [IQR]
 - Note: AUC is computed only for those completing the 24 week follow-up visit.
 - b. Compare change in visual acuity at 24 weeks from randomization between treatment groups
 - Perform Markov Chain Monte Carlo multiple imputation² on missing data (100 imputations) for change in visual acuity at 24 weeks using all available visual acuity data at post randomization follow-up visits, accounting for treatment group assignment, randomization visual acuity value, laterality and improvement in visual acuity during run-in phase. Create flags for binary outcomes specified above based on imputed data.

- ii. Primary analysis: Perform a linear mixed effects model for treatment group comparison of mean change in visual acuity at 24 weeks from randomization. (%*MIAnalyzeMeanMixed* macro)
 - Truncated change in visual acuity letter scores at 24 weeks will be fitted as the dependent variable, and the treatment group as the independent variable, adjusting for randomization visual acuity value, randomization stratification factors (laterality and improvement in visual acuity during run-in phase as defined in the protocol) by including each as a fixed effect in the model. A random subject effect will be included to adjust for the correlation between eyes of participants who have two randomized eyes (assuming a compound symmetry covariance structure).
 - Run the model on observed data to check model assumptions including residual analysis, goodness of fit and influence diagnostics [**not in text**]
 - Run the model on the imputed datasets and report the adjusted mean difference, 95% confidence interval, and *P*-value from treatment group comparison [**Table 2**]
 - Assessment of confounding: Impute the outcome accounting for additional pre-specified potential confounding factors, including age, duration of diabetes, HbA1c levels, retinal thickening on OCT, and diabetic retinopathy severity on clinical exam. All categorical covariates with more than 2 levels are collapsed to a binary covariate for modeling to aid convergence. Mimic primary analysis and obtain *P*-value for treatment group comparison.

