 - Mean \pm SD
 - Median [IQR]
 - Note: AUC is computed only for those completing the 24 week follow-up visit.
- b. Compare change in central subfield thickness (CST) at 24 weeks from randomization between treatment groups
 - i. Perform Markov Chain Monte Carlo multiple imputation² on missing data (100 imputations) for change in CST at 24 weeks using all available OCT CST data at post randomization follow-up visits, accounting for treatment group assignment, randomization visual acuity value, laterality and improvement in OCT CST during run-in phase. Create flags for binary outcomes specified above based on imputed data.
 - ii. Primary analysis: Perform a linear mixed effects model for treatment group comparison of mean change in CST at 24 weeks from randomization (%*MIAnalyzeMeanMixed* macro).
 - Truncated changes in CST at 24 weeks will be fitted as the dependent variable, and the treatment group as the independent variable, adjusting for randomization OCT CST, randomization stratification factors (laterality and improvement in OCT CST during run-in phase as defined in the protocol) by including each as a fixed effect in the model. A random subject effect will be included to adjust for the correlation between eyes of participants who have two randomized eyes (assuming a compound symmetry covariance structure).
 - Run the model on observed data to check model assumptions including residual analysis, goodness of fit and influence diagnostics [**not in text**]
 - Run the model on the imputed datasets and report the adjusted mean difference, 95% confidence interval, and *P*-value from treatment group comparison [**Table 2**]
 - Assessment of confounding: Impute the outcome accounting for additional pre-specified potential confounding factors, including age, duration of diabetes, HbA1c levels, and diabetic retinopathy severity on clinical exam. All categorical covariates with more than 2 levels are collapsed to a binary covariate for modeling to aid convergence. Mimic primary analysis and obtain *P*-value for treatment group comparison. [**not in the text**]
 - Per-protocol analysis [eTable 2]
 - As specified in the statistical analysis plan, the per-protocol analysis will mimic the primary analysis limiting the cohort to 24-week completers who had available data and received

all required injections at the completed visits without receiving any non-protocol treatment. No imputation will be performed.

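### The primary acuity model leaves most of the run-in acuity data unused: adding the mean of the three pre-randomization run-in readings would probably narrow the interval slightly at almost no cost

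*SAP*

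**What the plan says.** **Model.** SAP item 4.b.ii regresses truncated 24-week acuity change on treatment, "adjusting for randomization visual acuity value, randomization stratification factors (laterality and improvement in visual acuity during run-in phase as defined in the protocol"), with a random subject effect. Protocol 7.3.1 likewise names only the randomization-visit acuity as the baseline measurement.

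**Run-in flag.** Protocol 4.4 defines acuity improvement "as 5 or more letter gain in visual acuity at any run-in visit, compared with the prior" visit. It is a yes/no factor.

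**Readings collected.**
- Enrollment (Protocol 2.3.2): "Tester (including protocol refraction) in each eye. (within 8 days prior to enrollment").
- Weeks 4 and 8 (Protocol 3.3): "Electronic-ETDRS visual acuity testing at 3 meters using the Electronic Visual Acuity Tester in each eye, including protocol refraction in the study eye".
- Randomization visit (Protocol 4.3): the same test on the day of randomization.
- Protocol 4.2, item a, makes these visits a condition of randomization: "All 3 run-in phase visits and ranibizumab injections were completed within ± 10 days of the" target date.

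**Other uses.** The acuity imputation (SAP 4.b.i) works "using all available visual acuity data at post randomization follow-up visits", together with treatment group, randomization acuity, laterality and the run-in flag. The pre-specified confounding factors include no earlier acuity value. The continuous change from enrollment to randomization is listed only among the descriptive baseline characteristics.

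**Retinal thickness.** The central subfield thickness (CST) model in SAP 5.b.ii has the same structure: "adjusting for randomization OCT CST, randomization stratification factors (laterality and improvement in OCT CST during run-in phase as defined in the protocol").

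**The concern.** A single letter score measures an eye's pre-treatment level with error. Three further readings, taken over the preceding 12 weeks by the same method, carry information about that level which the randomization reading alone does not. The flag keeps little of it: it records whether any one step between visits reached 5 letters, says nothing about level, and can be set off by noise in one reading.

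Precision matters here because Protocol 7.1 and 7.3.1 frame the primary analysis as estimation of a difference, and Protocol 7.2 justifies the sample size with a table of 95% confidence interval half-widths. The subgroup analyses reuse the primary model, and Protocol 7.6 uses this trial's variability to plan the phase III trial. Any efficiency gain would carry into both.

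**Working it through.** **1. The plan's own figures.** Protocol 7.2 gives 70 evaluable eyes per group, SD 7 or 9, and a two-sided 95% interval. Half-width = 1.96 × SD × √(2/70).
- SD 7: 1.96 × 7 × 0.1690 = 2.32 (stated 2.3).
- SD 9: 1.96 × 9 × 0.1690 = 2.98 (stated 3.0).
- Power for 5 letters at SD 9: 5/(9 × 0.1690) = 3.29; 3.29 − 1.96 = 1.33; power 90.8% (stated 90%).

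All three reproduce. The source SD of 6.9 is already adjusted for one baseline acuity value, so these figures describe the single-baseline model.

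**2. Assumptions, none from the documents.** Between-eye SD 8 to 11 letters; test-retest SD 2.5 to 4.5; true drift SD 1 to 3 letters per 4 weeks. Mid-range: 11, 3.5 and 2. Eyes are treated as independent, as in the protocol's table. The residual SD under the planned model is set to 7 or 9.

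**3. Hand calculation at mid-range, without flag or eligibility limits.** Let M be the mean of the enrollment, week-4 and week-8 readings, X the randomization reading and T the true level at randomization.
- True-level variances at the four visits: 11² = 121, then +2² each step: 125, 129, 133.
- Var(X) = 133 + 3.5² = 145.25.
- Cov(M, T) = Cov(M, X) = (121 + 125 + 129)/3 = 125.
- Var(M) = [375 + 3 × 12.25 + 2 × (121 + 121 + 125)]/9 = 127.31.
- Cov(M, T given X) = 125 × 12.25/145.25 = 10.54.
- Var(M given X) = 127.31 − 125²/145.25 = 19.73.
- Variance removed by adding M = 10.54²/19.73 = 5.63. That is 5.63/49 = 11.5% at SD 7 and 5.63/81 = 7.0% at SD 9.

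**4. With the flag and the 24-to-78-letter limits (simulation).** The mid-range reduction is 10.0% at SD 7 and 6.1% at SD 9, a little below the hand calculation because the flag already takes a small share. In a second simulation, with between-eye SD 8 or 12, reading error 2 to 5 and drift 0 to 3, the flag alone moved the residual SD from 7.00 only to between 6.91 and 7.00. Over the ranges in step 2 the reduction is about 2 to 20% at SD 7 and 1.5 to 12% at SD 9.

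**5. Are the mid-range values consistent with the SD?** If drift continues over the six 4-week steps to week 24, residual variance is Var(T given X) + 6 × drift² + error².
- Drift 2: 133 × 12.25/145.25 + 24 + 12.25 = 47.5, SD 6.9. This fits SD 7.
- SD 9 with the same reading error needs drift of about 3.1: 149.83 × 12.25/162.08 + 57.66 + 12.25 = 81.2. The simulated reduction is then 4.1%, so 4 to 6% is the fair mid-range at SD 9.

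**6. Effect on the interval.**

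| Residual SD | Planned half-width | Variance reduction | Half-width after | Equivalent eyes per group |
|---|---|---|---|---|
| 7 | 2.32 | 10% | 2.32 × √0.90 = 2.20 | 70/0.90 = 77.8 |
| 7 | 2.32 | 2 to 20% | 2.30 to 2.07 | 71.4 to 87.5 |
| 9 | 2.98 | 4 to 6% | 2.92 to 2.89 | 72.9 to 74.5 |
| 9 | 2.98 | 1.5 to 12% | 2.96 to 2.80 | 71.1 to 79.5 |

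Power for 5 letters at SD 9 with a 6% reduction: 5/(9 × √0.94 × 0.1690) = 3.39; 3.39 − 1.96 = 1.43; 92.4% against 90.8%.

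**The case against.** The strongest reply is that nothing here is wrong. Randomization acuity plus stratification factors is a conventional covariate set that the protocol specified in advance, the estimator is valid, and the trial is a phase II study that does not claim to establish efficacy. The gain is about 0.1 letter of half-width and rests wholly on assumed noise and drift. All of that stands, and it sets the weight of the point.

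Three further objections also stand in part:
- **Timing.** The SAP document is a manuscript technical plan effective 9-25-2017, built on a database dated 21 September 2017. A new primary covariate at that stage would come after the data freeze. The separate protocol SAP that it cites is not among the documents.
- **Completeness.** A reader might infer that every randomized eye has all three readings. Protocol 4.2 makes this a rule, not a fact: the SAP's Site 194 sensitivity analysis records ineligible participants enrolled there. The covariate needs a rule for missing readings.
- **Not pure replicates.** The week-4 and week-8 readings follow ranibizumab injections and may trend. This is a reason to keep randomization acuity in the model, not to omit the run-in mean: its coefficient is estimated, and treatment assignment cannot affect it.

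A reader might also infer that the imputation ignores the run-in altogether. It does not, because SAP 4.b.i includes the flag. With about 5% loss planned and later acuity values already used, extra run-in data would add little there.

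**Conclusion.** The point holds as a modest loss of efficiency. The continuous run-in acuity readings are collected by design but reach the primary model only as a binary flag. Under the stated assumptions the half-width would move from 2.3 to about 2.2 letters at SD 7, or from 3.0 to about 2.9 at SD 9, equivalent to roughly 3 to 8 more eyes per group.

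Two stronger readings are not supported. One is that the planned interval or power statement is wrong, or the estimate biased: the stated figures reproduce and are right for a single-baseline model. The other is that a material narrowing is assured: the documents give no test-retest SD, drift or between-visit correlation, and the gain is near zero if reading error is negligible or true drift dominates. The calculation also leaves out two-eye correlation and truncation of the outcome at 3 SD. No size is claimed for CST, for which no variance figures are available.

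**What to change.** - **Model (SAP 4.b.ii, Protocol 7.3.1).** Keep randomization acuity, laterality and the run-in flag. Add one continuous fixed effect: the mean of the available enrollment, 4-week and 8-week acuity scores. Using available scores keeps an eye with a missing run-in reading in the analysis.
- **Imputation (SAP 4.b.i).** Add the same variable to the present terms.
- **If treatment comparisons have already been seen.** Leave the planned primary analysis as it is, report the extended model as a labelled supportive analysis, and use it in the phase III model.
- **CST (SAP 5.b.i and 5.b.ii).** The same addition can be considered with run-in CST. The imputation in 5.b.i should then also include randomization CST; at present it lists randomization visual acuity and not randomization CST.

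Cost: one model degree of freedom with about 140 evaluable eyes (2 × 70), and a wording change in the SAP and in Protocol 7.3.1. No new data are needed.

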803		• For study participants with two study eyes (both eyes eligible at the time of
804		randomization):
805 806		 The study participant will be randomized with equal probability to receive either: Group A in the eye with greater OCT improvement and Group B in the
800 807		eye with lower OCT improvement
808		 Group B in the eye with greater OCT improvement and Group A in the
809		eye with lower OCT improvement
810		ote: if both eyes have the same OCT improvement, the right eye will be consider the eye with
811 812	the	e greater improvement.

813	4.5 Randomization Treatment
-----	-----------------------------

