 - Post hoc assessment: impute the data with additional factors including lens status (pseudophakic vs. phakic) and number of anti-VEGF injections (3 vs. more than 3 injections) within 20 weeks prior to run-in. Mimic the prespecified analysis above by including each additional variable one at a time. [Table 2 Footnote]
 - Construct a scatter plot of number of prior anti-VEGF (as a continuous outcome) versus change in visual acuity at 24 weeks by treatment group to explore the potential relationship using observed data. [not in text]
 - Per-protocol analysis [eTable 2]
 - As specified in the statistical analysis plan, the per-protocol analysis will mimic the primary analysis limiting the cohort to 24-week completers who had available data and received all required injections at the completed visits without receiving any non-protocol treatment. No imputation will be performed.

- Report mean ± SD and median [IQR] by treatment group, adjusted mean difference, 95% CI and *P*-value from the treatment group comparison
- Sensitivity analysis [not in text]
 - All sensitivity analyses will mimic the primary analysis model using imputed data.
 - Pre-specified sensitivity analysis will be performed and stratified by sham injection procedure.
 - Post hoc sensitivity analysis will exclude all patients at Site 194.
 - Note: this was at recommendation of DSMC, after review of cases of ineligible participants enrolled at that site discovered at a site visit.
- Subgroup analysis (%*subgrpMixed* macro):
 - Pre-specified subgroup analysis will evaluate the effects of following baseline factors: lens status [eFigure 2], improvement in visual acuity during run-in phase [eFigure 3], and improvement in OCT during run-in phase [eFigure 4]. [eTable 3]
 - Post hoc subgroup analysis will mimic the pre-specified subgroup analysis to examine the effect of the following baseline factors: randomization visual acuity (<64 vs. ≥64 letters), and number of prior anti-VEGF injections within 20 weeks prior to run-in (3 vs. 4 or more injections). [eTable 4]
 - The subgroup analysis will mimic the primary analysis adding an interaction between subgroup and treatment to the primary mixed model using observed data only.
 - Report the *P*-value for the interaction term. Report mean ± SD and median [IQR] by treatment group within each subgroup.

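### Each of the SAP's two main models adjusts for only one of the two run-in factors used to stratify randomization, so the reported confidence interval may be slightly too wide

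*SAP*

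**What the plan says.** Protocol 4.4, for participants with one study eye: "Randomization will be stratified by two factors". The first is "Presence or absence of improvement in retinal thickness during the run-in phase", meaning a 10% reduction in CSF thickness at any run-in visit compared with the visit before. The second is a gain of at least 5 letters, judged the same way. Participants with two study eyes are allocated by ranking their eyes. One of the two equally likely assignments is "Group A in the eye with greater OCT improvement and Group B in the" other eye, so acuity improvement plays no part for them.

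The SAP's acuity model (item 4.b.ii) adjusts for randomization acuity and "randomization stratification factors (laterality and improvement in visual acuity during run-in phase as defined in the protocol". Its imputation model (4.b.i) is specified as "accounting for treatment group assignment, randomization visual acuity value, laterality and improvement in visual acuity during run-in phase". The CST model (5.b.ii) adjusts for randomization CST and "randomization stratification factors (laterality and improvement in OCT CST during run-in phase as defined in the protocol", with imputation (5.b.i) "accounting for treatment group assignment, randomization visual acuity value, laterality and improvement in OCT CST during run-in phase". The binary secondary outcomes reuse the primary covariates, and the order for dropping covariates on non-convergence lists one run-in factor per outcome. The per-protocol, sensitivity and AUC analyses copy the primary model.

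Protocol 7.3.1 refers to a stratification factor in the singular and does not name it.

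**The concern.** The SAP says its covariates are the protocol's stratification factors, but neither model contains the set that Protocol 4.4 defines. In the acuity model, which gives the primary result, the missing factor is thickness improvement. Thickness improvement stratifies the one-eye participants, and it is also the only run-in measure used to allocate two-eye participants.

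Stratification balances a factor between arms and so reduces the true sampling variability of the treatment difference. A model that leaves the factor out does not credit that reduction, and its standard error is too large if the factor is prognostic. Protocol 7.1 defines the primary analysis as estimation of a difference, and Protocol 7.6 feeds the resulting variability into phase III planning. The width of the interval is therefore a main product of this trial.

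**Working it through.** **Is the factor restored elsewhere?** No. The subgroup analyses bring it in by "adding an interaction between subgroup and treatment to the primary mixed model using observed data only", which leaves the primary estimate unchanged. The confounding assessment for acuity includes retinal thickening on OCT, but that is not improvement during run-in. The confounding list for CST contains no acuity measure.

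**Reproducing the plan's figures.** Inputs from Protocol 7.2: 70 eyes per group, two-sided 95% CI, SD 7 or 9.

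- Half-width = 1.96 × SD × sqrt(2/70).
- SD 7: 2.32 (protocol 2.3). SD 9: 2.98 (protocol 3.0).
- Power for 5 letters at SD 9: 0.908 (protocol 90%).

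**Effect of the omission.** Let R² be the share of residual variance that the omitted factor explains after baseline value, laterality and the included factor. The documents give no value, so a range is assumed.

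- SE ratio, omitted to included = 1/sqrt(1 − R²).
- Half-width with the factor included = 1.96 × SD × sqrt(2/70) × sqrt(1 − R²).
- Gap between factor levels that gives R² at an even split = 2 × SD × sqrt(R²).

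| Assumed R² | SE ratio, formula | SE ratio, simulation | Half-width, SD 9 | Half-width, SD 7 | Gap needed at SD 9 (letters) |
|---|---|---|---|---|---|
| 0 | 1.000 | 0.999 | 2.98 | 2.32 | 0 |
| 0.01 | 1.005 | 1.004 | 2.97 | 2.31 | 1.8 |
| 0.05 | 1.026 | 1.025 | 2.91 | 2.26 | 4.0 |
| 0.10 | 1.054 | 1.053 | 2.83 | 2.20 | 5.7 |

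The simulation used 6,000 trials per setting, with 100 one-eye participants in permuted blocks within the four strata and 25 two-eye participants allocated by ranking. A random-subject model was fitted. It assumed blocks of 4, 50% prevalence of each factor, correlation 0.3 between the factors and 0.3 between eyes. The mean estimated difference stayed within 0.002 SD of zero.

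**Type I error.** Null rejection in that simulation, factor omitted versus included, was 5.4 v 5.5%, 5.7 v 5.8%, 4.7 v 4.8% and 5.0 v 5.6% in the order of the table rows (Monte Carlo SE about 0.3 points). Omission never raised the rate. A further simulation of the mixed one-eye and two-eye design gave about 4.4% omitted against 4.8 to 4.9% included.

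**Coverage in a stronger case.** A separate simulation at SD 7 with a 5-letter factor effect (R² about 0.13) and the factor omitted gave a mean model SE of 1.073 against an empirical SD of 1.030, and coverage of 95.9%. The half-width was 2.12 with the factor omitted and 1.98 with both included. With no factor effect the two models agreed.

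No CST half-width is given, because the documents state no SD for CST change.

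**The case against.** The strongest reply is that the effect is small and conditional. Reaching R² = 0.10 at SD 9 needs a 5.7-letter gap between factor levels after the other covariates, which exceeds the 5-letter treatment difference used for power. Even a 5-letter gap at an even split raises power only from 0.908 to 0.928. This stands, and it limits the size of the point.

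Second, two-eye participants are not stratified on either binary factor. At the planned 20% they supply 50 of 150 eyes, and for them the loss is mainly precision rather than over-coverage. This also stands. The simulations include them, and the direction does not change.

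Third, the claim of a conservative test can be questioned. In the main simulation the rejection rate at R² = 0.10 with the factor omitted was 5.0%, whereas complete balance on the factor would predict about 3.9%. That run alone does not establish conservatism in absolute terms. The lower rate under omission in the further simulation and the 95.9% coverage in the stronger case support a slight effect.

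Fourth, Protocol 7.4.1 asks only for baseline adjustment of continuous secondary outcomes, and CST is secondary. The singular wording in Protocol 7.3.1 might also be read as allowing one factor for acuity. Neither explains why the SAP describes its covariates as the protocol's stratification factors, or why a different one is chosen for each outcome.

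Finally, the supplied plan is the manuscript technical plan. It points to a separate protocol SAP that was not supplied and may give a reason.

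**Conclusion.** The point holds. Each model omits one of the two factors by which one-eye participants are randomized, and nothing in the supplied text puts it back into the primary estimate. If the omitted factor is prognostic, the SE is about 0.5% to 5.4% too large over the assumed R² range of 0.01 to 0.10. At SD 9 that is at most 0.15 letters of half-width (2.98 − 2.83). If it is not prognostic, nothing changes. There is no bias and no type I error inflation.

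The sizes rest on assumed prognostic strength. They also apply the protocol's SD, which is adjusted for baseline acuity only, as an approximation to the residual SD after laterality and the included factor. The simulations had no missing data, so they do not test the imputation models; planned loss is only about 5%. The change is worth making because it is nearly free, but the trial's conclusions are unlikely to turn on it.

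**What to change.** - In SAP items 4.b and 5.b, enter both run-in factors, as defined in Protocol 4.4, together with laterality as fixed effects in the acuity and CST models.
- Put both factors in both imputation models.
- Give the added factor a stated position in both covariate-removal hierarchies (4.b.iii and 5.b.iii).
- In Protocol 7.3.1, use the plural and name the factors.

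The technical plan took effect on 9-25-2017 and uses a database dated 21 September 2017. If results have already been seen, report the two-factor model beside the planned one and label it as added later. If the single-factor choice is deliberate, the SAP should say why and stop describing the covariates as the protocol's stratification factors.

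The cost is wording, one degree of freedom per continuous model and one more entry in each hierarchy. The binary models already anticipate non-convergence, and another covariate adds to that risk, which is why its removal order must be stated. Both variables are already collected and used for randomization and subgroup analysis.
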